## 7. Initial Feasibility Analysis

Action report name:

For degarelix vs. leuprolide

Optum CDM- <https://bwh-dope.aetion.com/projects/details/1636/rwrs/67085>

IBM® MarketScan®- <https://bwh-dope.aetion.com/projects/details/1323/rwrs/67083>

CMS Diabetes - <https://bwh-dope.aetion.com/projects/details/1637/rwrs/67081>

Date conducted: 03/06/2021

Complete Aetion feasibility analysis using age as the only covariate and the primary endpoint (Section 6.3.1) as the outcome. No measures of association will be computed, nor will incidence rates be stratified by treatment group.

- Report patient characteristics by treatment group
  - Degarelix vs Leuprolide

	Optum CDM			IBM® MarketScan®			CMS - Diabetes		
Variable	Leuprolide - Comparator	Degarelix - Exposure	Difference	Leuprolide - Comparator	Degarelix - Exposure	Difference	Leuprolide - Comparator	Degarelix - Exposure	Difference
Number of patients	3,676	596		2,936	431		5,828	941	
Age									
...mean (sd)	75.71 (7.42)	75.93 (7.66)	-0.22 (-0.88, 0.44)	74.38 (9.05)	74.49 (9.12)	-0.11 (-1.03, 0.82)	76.85 (6.58)	76.94 (6.49)	-0.09 (-0.53, 0.36)
...median [IQR]	76.00 [71.00, 81.00]	76.00 [71.00, 82.00]		75.00 [68.00, 81.00]	75.00 [68.00, 82.00]		76.00 [72.00, 81.00]	77.00 [72.00, 81.87]	

- Report summary parameters of study population **FEASIBILITY- FOR STUDY OUTCOME**
  - For Degarelix vs Leuprolide

FEASIBILITY FOR STUDY OUTCOME			
	Optum CDM	IBM® MarketScan®	CMS - Diabetes
Number of patients in full cohort	4,278	3,369	6,770
Number of patients dropped as incomplete cases	0	0	0
Number of patients that did not begin follow-up	6	2	1
Number of patients in analytic cohort	4,272	3,367	6,769
Number of events	108	43	211
Number of person-years	1,259.68	1,001.03	2,031.94
Number of patients in group: Leuprolide - Comparator	3,676	2,936	5,828
Number of patients in group: Degarelix - Exposure	596	431	941
Risk per 1,000 patients	25.28	12.77	31.17
Rate per 1,000 person-years	85.74	42.96	103.84

- Report median follow-up time by treatment group
  - For Degarelix vs Leuprolide

FOLLOW-UP TIME FOR STUDY OUTCOME			
Median Follow-Up Time (Days) [IQR] – At 90 days gap			
Patient Group	Optum CDM	IBM® MarketScan®	CMS - Diabetes
Overall Patient Population	89 [89, 89]	89 [89, 89]	89 [89, 89]
Referent - Leuprolide	89 [89, 89]	89 [89, 89]	89 [89, 89]
Exposure - Degarelix	82 [33, 132]	68 [31, 126]	67 [32, 124]

- Report reasons for censoring in the overall study population
  - For Degarelix vs Leuprolide

CENSORING REASONS FOR STUDY OUTCOME			
Reasons	Optum CDM	IBM® MarketScan®	CMS - Diabetes
Outcome	108 (2.5%)	43 (1.3%)	211 (3.1%)
Start of an additional exposure	351 (8.2%)	256 (7.6%)	584 (8.6%)
End of index exposure	3,344 (78.3%)	2,674 (79.4%)	5,277 (78.0%)
Maximum follow-up time	118 (2.8%)	94 (2.8%)	205 (3.0%)
Specified date reached	182 (4.3%)	52 (1.5%)	270 (4.0%)
End of patient data	0 (0.0%)	0 (0.0%)	0 (0.0%)
End of patient enrollment	169 (4.0%)	248 (7.4%)	222 (3.3%)

- Report overall risk of the primary outcome.

	Optum CDM	IBM® MarketScan®	CMS - Diabetes	Pooled
Risk per 1,000 patients	25.28	12.77	31.17	25.12

## 8. Initial Power Assessment

Action report name:

- For Degarelix vs Leuprolide
  - Optum CDM- <https://bwh-dope.aetion.com/projects/details/1636/rwrs/67086>
  - IBM® MarketScan®- <https://bwh-dope.aetion.com/projects/details/1323/rwrs/67084>
  - CMS Diabetes - <https://bwh-dope.aetion.com/projects/details/1637/rwrs/67082>

Date conducted:

In order to complete the initial power analysis, a dummy outcome indicating a 90-day gap in database enrollment will be used. This outcome is used to ensure that no information on the comparative risks of the outcomes of interest are available at this stage. A 1:1 PS-matched comparative analysis was performed, including age as the only covariate. Power calculations are based on the formulas

from Chow et al. (2008).

- Stop analyses until feasibility and power are reviewed by primary investigators and FDA. Reviewers evaluate the results of the analyses described above in Sections 7 and 8, including numbers of patients, patient characteristics, follow-up time, and reasons for censoring by treatment group, as well as overall rates of outcomes and study power. These parameters are re-evaluated and reported in the subsequent sections, after incorporating feedback and refining the protocol.

- Pooled

Superiority Analysis	
Number of patients matched	3,934
Reference	1,967
Exposed	1,967
Risk per 1,000 patients	25.12
Desired HR from RCT	0.49
Alpha (2-sided)	0.05
Number of events expected	98.82208
Power	0.943598201

- Optum CDM

Superiority Analysis	
Number of patients matched	1,192
Reference	596
Exposed	596
Risk per 1,000 patients	25.28
Desired HR from RCT	0.49
Alpha (2-sided)	0.05
Number of events expected	30.13376
Power	0.499237002

- IBM® MarketScan®

Superiority Analysis	
Number of patients matched	862
Reference	431
Exposed	431
Risk per 1,000 patients	12.77
Desired HR from RCT	0.49
Alpha (2-sided)	0.05
Number of events expected	11.00774
Power	0.21953525

- CMS - Diabetes

Superiority Analysis	
Number of patients matched	1,880
Reference	940
Exposed	940
Risk per 1,000 patients	31.17
Desired HR from RCT	0.49
Alpha (2-sided)	0.05
Number of events expected	58.5996
Power	0.779468883

Stop analyses until feasibility and power are reviewed by primary investigators, FDA, and assigned members of advisory board.

Reviewed by PI:	[name]	Date reviewed:	3/17/2021
Reviewed by FDA:	[name]	Date reviewed:	4/3/2021
Reasons for stopping analysis (if required):			

## 9. Balance Assessment

Action report name:

For Degarelix vs. leuprolide

Optum CDM- <https://bwh-dope.aetion.com/projects/details/1636/rwrs/68435>

IBM® MarketScan®- <https://bwh-dope.aetion.com/projects/details/1323/rwrs/68424>

CMS Diabetes - <https://bwh-dope.aetion.com/projects/details/1637/rwrs/68434>

Date conducted: 04/14/2021

After review of initial feasibility and power analyses, complete creation of the remaining covariates from Section 6.2. Again, using the dummy outcome of a 90-day gap in database enrollment, complete a 1:1 PS-matched analysis. The PS should include the complete list of covariates.

- Provide plot of PS distributions stratified by treatment group.

Note- Please refer to Appendix\_Table1\_PRONOUNCE\_v1 (worksheet named 'PS matching').

- Report covariate balance after matching.

Note- Please refer to Appendix\_Table1\_PRONOUNCE\_v1 (worksheet named 'Table 1').

- Report reasons for censoring by treatment group.

	Overall	Referent	Exposure
Start of an additional exposure	1147 (30.39%)	1 (0.05%)	1146 (60.73%)
End of index exposure	2084 (55.22%)	1645 (87.18%)	439 (23.26%)
Specified date reached	157 (4.16%)	78 (4.13%)	79 (4.19%)
Maximum follow-up reached (365 days)	142 (3.76)	42 (2.23%)	100 (5.30%)
End of patient enrollment	244 (6.46%)	121 (6.41%)	123 (6.52%)

- Report follow-up time by treatment group.

Patient Group	Median Follow-Up Time (Days) [IQR]		
	Optum CDM	IBM® MarketScan®	CMS - Diabetes
Overall Patient Population	89 [64, 116]	89 [55, 118]	89 [61, 109]
Referent	89 [89, 89]	89 [89, 89]	89 [89, 89]
Exposure	82 [33, 140]	67 [31, 126]	68 [33, 125]

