## 10. Final Power Assessment

Date conducted: 4/15/2021

Re-calculate power in the appropriate excel table, using the revised number of matched patients from the PS-match in Section 9. All other parameters in the table should be the same as in Section 8.

- Pooled

Superiority Analysis	
Number of patients matched	3,774
Reference	1,887
Exposed	1,887
Risk per 1,000 patients	25.12
Desired HR from RCT	0.49
Alpha (2-sided)	0.05
Number of events expected	94.80288
Power	0.93484302

- Optum CDM

Superiority Analysis	
Number of patients matched	1,092
Reference	546
Exposed	546
Risk per 1,000 patients	25.28
Desired HR from RCT	0.49
Alpha (2-sided)	0.05
Number of events expected	27.60576
Power	0.465815489

- IBM® MarketScan®

Superiority Analysis	
Number of patients matched	830
Reference	415
Exposed	415
Risk per 1,000 patients	12.77
Desired HR from RCT	0.49
Alpha (2-sided)	0.05
Number of events expected	10.5991
Power	0.21311438

- CMS - Diabetes

Superiority Analysis	
Number of patients matched	1,852
Reference	926
Exposed	926
Risk per 1,000 patients	31.17
Desired HR from RCT	0.49
Alpha (2-sided)	0.05
Number of events expected	57.72684
Power	0.773370349

- Stop analyses until balance and final power assessment are reviewed by primary investigators, FDA, and assigned members of advisory board.

Reviewed by PI:		Date reviewed:	
Reviewed by FDA:		Date reviewed:	
Reasons for stopping analysis (if required):			

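### At the assumed hazard ratio of 0.49 the 1:1 match yields about 76 events, not 94.8, so pooled power is about 0.87 rather than 0.935; matching up to 1:3 would regain some precision, but only modestly

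*Combined protocol and SAP*

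**What the plan says.** Section 9 asks the team to "complete a 1:1 PS-matched analysis" with the full covariate list, run on a dummy outcome. Section 8 explains the dummy outcome: "This outcome is used to ensure that no information on the comparative risks of the outcomes of interest are available at this stage". Table 1 in the appendix shows 12,448 leuprolide and 1,969 degarelix men before matching, and 1,887 of each afterwards.

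The pooled table in Section 10 reads "Number of patients matched 3,774", "Risk per 1,000 patients 25.12", "Desired HR from RCT 0.49", "Alpha (2-sided) 0.05", "Number of events expected 94.80288" and "Power 0.93484302". Stated power by database is 0.466 (Optum), 0.213 (MarketScan) and 0.773 (CMS).

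The document gives no reason for 1:1, no caliper and no alternative ratio or weighting. Section 13, where the comparative model would be described, is empty.

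**The concern.** Two linked matters affect how precise the pooled hazard ratio will be.

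First, two inputs in Section 10 do not fit together. The risk of 25.12 per 1,000 is the overall risk in a cohort that is 86% leuprolide. If degarelix halves the hazard, a sample that is half degarelix must have a lower overall risk. Using 25.12 for both arms overstates the events, and so the power, that reviewers are asked to accept.

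Second, there are about six leuprolide men for each degarelix man, and 1:1 uses only one of them. Balance is judged before any comparative outcome is seen, so a higher ratio could be accepted or rejected on balance alone. That removes much of the usual reason for staying at 1:1.

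At stake are the stated power and the width of the final interval. The single databases, where stated power is already low, are affected most.

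**Working it through.** **Inputs.**
- Section 7: 362 events (108 + 43 + 211) in 14,408 analysed men (4,272 + 3,367 + 6,769), which gives 25.12 per 1,000. Of these men, 1,968 (596 + 431 + 941) took degarelix, a share of 0.1366.
- Section 10: 1,887 men per arm, hazard ratio 0.49, two-sided alpha 0.05.
- Table 1: 12,448 leuprolide men before matching.

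**Reproducing the plan's figure.** Power = Φ(|ln HR| × √(d/4) − 1.96).
- Events: d = 3,774 × 0.02512 = 94.80.
- Power: 0.7133 × 4.868 − 1.96 = 1.513, and Φ(1.513) = 0.935. This agrees with Section 10.
- All eight power tables in Sections 8 and 10 reproduce to within 0.001, so the formula is not in dispute.

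**Events consistent with a hazard ratio of 0.49.** Treat the hazard ratio as a risk ratio (events are rare) and assume equal follow-up.
- Leuprolide risk = 25.12 / (0.8634 + 0.1366 × 0.49) = 27.0 per 1,000. Degarelix risk = 0.49 × 27.0 = 13.2 per 1,000.
- Degarelix events = 1,887 × 0.01323 = 25.0. Leuprolide events = 1,887 × 0.0270 = 51.0. Total = 75.9.
- Protocol formula: 0.7133 × √(75.9/4) − 1.96 = 1.148, so power is 0.87.
- Wald: SE = √(1/25.0 + 1/51.0) = 0.244, and Φ(0.7133/0.244 − 1.96) = 0.83.

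**By database** (same steps with each database's own risk and degarelix share, protocol formula):

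| Database | Events stated | Events recomputed | Power stated | Power recomputed |
|---|---|---|---|---|
| Optum | 27.6 | 22.1 | 0.466 | 0.39 |
| MarketScan | 10.6 | 8.4 | 0.213 | 0.18 |
| CMS | 57.7 | 46.3 | 0.773 | 0.68 |

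**Effect of the matching ratio.** Hold 1,887 degarelix men fixed with k leuprolide men each. SE = √(1/d₁ + 1/d₀).

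| Ratio | SE at HR 0.49 | Wald power at HR 0.49 | SE at HR 1 |
|---|---|---|---|
| 1:1 | 0.244 | 0.83 | 0.205 |
| 1:2 | 0.223 | 0.89 | 0.178 |
| 1:3 | 0.216 | 0.91 | 0.168 |
| All 12,448 | 0.207 | 0.93 | 0.156 |

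The log-scale interval narrows by 1 − 0.216/0.244 = 12% at a hazard ratio of 0.49, and by 1 − 0.168/0.205 = 18% at 1. Full 1:3 recovers about 79% of the variance lost relative to using every leuprolide man. An average ratio of 1:2 recovers 59%.

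**Is 1:3 attainable?** The ratio available is 12,448 / 1,887 = 6.6. Without the 927 leuprolide men who entered in 2008–2009, when no degarelix man did, it is 11,521 / 1,887 = 6.1. Pre-match c-statistics are 0.669 to 0.719. A simulation assuming a normal linear propensity score with those c-statistics, and calipers of 0.001 to 0.01, reached an average of 2.7 to 2.8 leuprolide men per matched degarelix man.

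**Which analysis keeps the gain?** Section 9 shows leuprolide follow-up of 89 [89, 89] days, and degarelix medians of 67 to 82 days with lower quartiles of 31 to 33. In a Cox model stratified on matched set, an event counts only if a man from the other arm of the same set is still at risk. Rough simulations with follow-up set to those quartiles, a hazard ratio of 0.49 and full sets gave these SEs:
- set-stratified 1:3: 0.27 to 0.29
- unstratified 1:1: 0.25 to 0.27
- unstratified 1:3: 0.22 to 0.23

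**The case against.** The strongest reply is that 1:1 is a recognised bias–precision choice and that no target is missed. The only power target in the document is the trial's 80% (Section 1.4), and pooled power stays above that on either recalculation. This stands: choosing 1:1 is not an error.

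A reader might infer from the counts that most of the information is lost, since 10,561 of 12,448 leuprolide men (85%) go unused. The figures do not support that. At 1:1 the leuprolide arm contributes only about a third of the variance (0.0196 of 0.0597), and some of the unused men have no calendar-time counterpart.

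A reader might also infer that the fall from 0.935 to 0.87 or 0.83 is caused by 1:1 matching. It is not. It comes from applying one pooled risk to both arms and, for the lower figure, from using the Wald variance under the alternative. The ratio is a separate question of efficiency.

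Overlap cannot be judged from c-statistics alone, and the score plots are not available here. Even at 1:1, 51 of 597 Optum degarelix men were not matched, and MarketScan glucose tests (0.13) and bisphosphonates (0.11) exceed 0.10. Whether 1:3 would pass a balance rule is therefore unknown, which is why adoption has to be conditional.

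Finally, a higher ratio does nothing about the differential censoring in Section 9, where 60.73% of degarelix men but 0.05% of leuprolide men were censored at the start of an additional exposure. That stands as a separate and arguably larger problem.

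**Conclusion.** The point holds in two parts of different weight.

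The stated pooled power is too high under the plan's own hazard ratio. About 76 events are expected rather than 94.8, and power is about 0.87 (Wald 0.83) rather than 0.935. In the single databases it is about 0.39, 0.18 and 0.68. This rests on the pooled risk applying to the matched men and on equal follow-up. Follow-up in fact differs between arms, so the event counts are approximate.

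The precision available from a higher ratio is real but modest: an interval about 12% to 18% narrower if full 1:3 is reached, and less otherwise. It is worth taking only if balance holds and the analysis does not stratify on matched set. The document does not support calling the study underpowered or the 1:1 design wrong.

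**What to change.** 1. In Section 10, replace the single pooled risk with arm-specific risks implied by the assumed hazard ratio, and restate expected events and power, pooled and by database. Section 8 uses the same input and needs the same note.
2. In Section 9, still on the dummy outcome, run variable-ratio matching of up to three leuprolide men per degarelix man within each database. Use the caliper applied for 1:1, and state it. Recompute standardized differences with matching weights.
3. Adopt the higher ratio only in databases where every covariate is at or below 0.10, or no worse than at 1:1. Otherwise keep 1:1 there.
4. In Section 13, specify a Cox model weighted by the matching weights, stratified by database only, with robust standard errors. Do not stratify on matched set. Keep 1:1 as a sensitivity analysis.

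The cost is a rerun of the matching, balance and power tables, and a few lines of text, before the Section 10 review, whose date fields are blank. No outcome comparison is touched. The downside is that second and third matches may be slightly less close. The differential censoring needs its own remedy.

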## Appendix A

**Optum****MarketScan****Medicare**

All variables under Table 1 is used in PS matching except Radiation therapies used in Prostate cancer, Chemo therapies used in Prostate cancer and Lithium

All variables under Table 1 is used in PS matching except HIV/AIDS, Radiation therapies used in Prostate cancer, Chemo therapies used in Prostate cancer and Lithium

All variables under Table 1 is used in PS matching except Lithium

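### No Optum man without a listed race remains in the matched cohort; up to 37 of the 50 degarelix men lost at the full PS match appear to be incomplete cases, and the plan neither states a rule nor gives a count

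*Combined protocol and SAP*

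**What the plan says.** Section 9 calls for a 1:1 PS match after the remaining covariates have been built: "The PS should include the complete list of covariates". The appendix note on the Optum model reads "All variables under Table 1 is used in PS matching except Radiation therapies used in Prostate cancer, Chemo therapies used in Prostate cancer and Lithium". Race is not among these exceptions, so it is in the Optum PS.

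Section 10 then recalculates power "using the revised number of matched patients from the PS-match in Section 9", with 546 Optum pairs and 1,887 pooled pairs. With age as the only covariate, Section 8 had 596 Optum pairs.

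The feasibility output in Section 7, also with age as the only covariate, has a row "Number of patients dropped as incomplete cases", which is 0 in all three databases. Sections 9 and 10 give no such row for the full-covariate run, and no section says how a missing covariate value is handled. In Table 1 for Optum, four race groups carry counts. The North American Native and Other rows show only dashes, before and after matching.

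**The concern.** A propensity model that includes a covariate with blanks needs a rule for the blanks. Without one, software commonly deletes the record before any matching takes place. In Optum the exposed arm is the scarce one (597 degarelix against 3,681 leuprolide), so each degarelix man deleted this way costs a pair. The matched Optum cohort would also be restricted to men with recorded race, a condition that appears nowhere in the eligibility criteria. Those deciding in Section 10 whether to proceed would see one reduced count and could not tell deletion from failure to find a match.

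**Working it through.** **Inputs.** Optum columns of Table 1 Unmatched and Table 1 Matched; analytic cohort sizes in Section 7; pair counts, risks and power in Sections 8 and 10.

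**1. The plan's own power.** Expected events = matched patients × risk. Power = Φ(½·√events·|ln HR| − 1.96), with HR 0.49 from the row "Desired HR from RCT" and two-sided alpha 0.05.
- Optum: 1,092 × 0.02528 = 27.61 events, power 0.4658 (stated 0.4658).
- Pooled: 3,774 × 0.02512 = 94.80 events, power 0.9348 (stated 0.9348).

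**2. Listed race before matching (White + Asian + Black + Hispanic).**
- Degarelix: 448 + 11 + 62 + 39 = 560 of 597, so 37 unlisted (6.2%).
- Leuprolide: 2,727 + 75 + 346 + 228 = 3,376 of 3,681, so 305 unlisted (8.3%).

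**3. Listed race after matching.**
- Degarelix: 438 + 11 + 61 + 36 = 546 of 546.
- Leuprolide: 437 + 8 + 66 + 35 = 546 of 546.

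Two printed percentages do not fit their counts (8 shown as 0.5%, 61 as 11.5%) and look like PDF-reading errors. The counts can be cross-checked with the Medicare and pooled columns: White 437 + 796 = 1,233 and 438 + 803 = 1,241; Black 66 + 93 = 159 and 61 + 85 = 146. For the 8 Asian men, the printed standardised difference of 0.04 agrees: |8/546 − 11/546| = 0.0055, divided by a pooled SD of 0.131, is 0.04.

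**4. Could this be chance?** If selection ignored race, 37 × 546/597 = 33.8 unlisted degarelix men and 305 × 546/3,681 = 45.2 unlisted leuprolide men would be expected in the matched arms. The hypergeometric probability of none is about 1e-47 and 5e-23.

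**5. Could it be a shortage of controls?** There were 305/37 = 8.2 unlisted leuprolide men per unlisted degarelix man, against 3,376/560 = 6.0 among listed men. So no.

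**6. Loss among men with listed race.** 560 − 546 = 14 of 560 (2.5%). This is in line with MarketScan (431 − 415 = 16, 3.7%) and Medicare (941 − 926 = 15, 1.6%). The White share of degarelix men rises from 75.0% to 80.2% on matching; removing the unlisted men alone gives 448/560 = 80.0%.

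**7. Share of the loss.** Table 1 has 597 degarelix men, but Section 7 has 596 who began follow-up. The loss at the match is therefore 596 − 546 = 50. The unlisted men are up to 37 of these (74%), or 36 (72%) if the man who never began follow-up was one of them.

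**8. Region.** Optum regions sum to 99 + 143 + 221 + 131 = 594 of 597 degarelix men and 366 + 1,037 + 1,352 + 925 = 3,680 of 3,681 leuprolide men before matching. After matching, the leuprolide rows sum to 546. The degarelix rows sum to 547, one too many; the cell printed as 132 (24.0%) fits 131. Up to 3 degarelix men may therefore have been dropped for missing region, and they may be among the 37.

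**9. Power if the men are kept** (plan's risks, existing pairs assumed unchanged).
- All 37 matched: Optum 1,092 + 74 = 1,166 patients, 29.48 events, power 0.491. Pooled 3,774 + 74 = 3,848 patients, 96.66 events, power 0.939.
- At the 97.5% match rate of listed men: 37 × 0.975 ≈ 36 pairs, power 0.490 and 0.939.

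**The case against.** The arithmetic is hard to dispute, but several stronger readings are tempting and the documents do not carry them.

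- **That the men are shown to have been deleted for a blank race code.** No section says so. The dashed Native and Other rows leave open an unprinted category. Its complete disappearance from both arms would still need an explanation, and deletion is the likeliest, but it remains an inference. This objection stands.
- **That the restriction is concealed.** Section 9 refers to a platform report and a workbook that are not reproduced in full. The same platform prints an incomplete-case row in Section 7, so the full run may have produced one too. What can be said is that the protocol text gives neither the rule nor the count.
- **That the effect estimate is biased, or that missing race is unrelated to drug and endpoint.** Neither is shown. The unlisted share differs somewhat by arm (6.2% and 8.3%), and no outcomes are given by race.
- **That overlap is made to look worse.** Overlap is judged from the PS plots and c-statistics, not from the pair count. Section 10's description of its count is literally correct; it does not say why men were lost.
- **That MarketScan sets a precedent for omitting race.** Its race rows are dashes, but its model note does not list race as an exception.

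It is also fair to say that complete-case analysis is a recognised choice and that the power gain alters no decision. That limits the importance of the point. It does not excuse leaving the choice unstated, or giving up exposed men who can be kept at almost no cost.

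**Conclusion.** The point holds as a probable, undocumented complete-case restriction in the Optum match. The counts are firm: 37 and 305 men without a listed race before matching, none after. The mechanism is inferred from the emptying of both arms, the ample controls and the low loss among listed men. Unlisted men explain up to 37 of the 50 degarelix men lost at the full match. Missing region may explain up to 3, possibly the same men.

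The cost in precision is modest: at most 37 pairs from race, or +6.8% of Optum pairs (37/546) and +2.0% of pooled pairs (37/1,887). Power rises by about 2.5 points in Optum, which stays near 0.49, and by about 0.4 points pooled. These figures assume the plan's risks and hazard ratio, and that a refitted PS leaves the existing pairs intact. The larger issue is that the analysed Optum population differs from the eligible one for a reason the protocol does not give.

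**What to change.** In the Optum PS, code missing race and missing region each as an Unknown category, so that no eligible man is dropped for either. Rerun the Optum match, balance table, censoring table and follow-up table before any comparative result is seen. The Section 10 review fields and Section 13 are still blank, so there is room to do this. Update the Optum and pooled counts and power in Sections 9 and 10. State the rule for missing covariates, and report for each database and arm the men dropped for incomplete covariates separately from men left unmatched. If the unlisted men were lost for some other reason, that count will show it.

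The cost is two recoded covariates and one rerun. The drawback is that, for about 6–8% of Optum men, race is balanced only as Unknown.
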